Day (D)	D-20 to 0	D1 ^{b,pp}	D2	D3	D8 ^{pp}	D10	D15	D16	D19	D20	D26	D33	D40	D47	D54	D61	D64	D82		
Day (D)		D85	D86	D87	D92	D94	D99	D100	D103	D104	D110									
Central Laboratory Tests (continued)																				
Core or incisional/excisional lymph node biopsy for biomarker analysis (optional) ^{oo}	X ⁿⁿ																	X ⁿⁿ		
MRD by NGS (plasma) ^{oo}		X							X				X					X		

Page 3 of 3

AE = adverse event; CBC = complete blood count; CNS = central nervous system; CR = complete remission; CSF = cerebrospinal fluid; CT = computed tomography; DLBCL = diffuse large B-cell lymphoma; ECOG = Eastern Cooperative Oncology Group; FDG = fluorodeoxyglucose; FU = follow-up; HBc = hepatitis b core; HBs = hepatitis b surface; HBsAg = hepatitis b surface antigen; HBV = hepatitis b virus; HSCT = hematopoietic stem cell transplantation; IV = intravenous; LTFU = long-term follow-up; MRD = minimal residual disease; MRI = magnetic resonance imaging; MTD = maximum tolerated dose; NGS = next generation sequencing; PET = positron emission tomography; PK = pharmacokinetics; SAE = serious adverse event

^a Safety follow-up will occur 30 days (+7 days) after last dose of each protocol specified therapy. If a subject starts a new anti-lymphoma treatment within 30 days of their last dose of protocol-assigned therapy, a safety follow-up visit should be conducted immediately prior to starting any new treatment, including HSCT conditioning regimens.

^b All procedures completed on first day of study treatment must be completed prior to the initiation of protocol-required therapy.

^c The initial dose of blinatumomab will be 9 µg/day and the dose will be escalated at weekly intervals until the target dose is reached. See Figure 1. For subjects that experience a blinatumomab dose interruption during cycle 1, subjects should resume the schedule of assessments following D85-110 procedures on Table 7-3 at the start of cycle 2.

^d Pembrolizumab will be administered starting on study day 19 (21-day cycles). See Section 6.2.2. Pembrolizumab may be administered up to 3 days before or after each scheduled day 1 from pembrolizumab cycle 2 onwards. For pembrolizumab dosing past cycle 5, see Table 7-4.

^e Vital signs should be monitored continuously every 4 hours during the first 12 hours after the start of each new treatment/dose step.

^f Height to be measured at screening only. Weight to be measured at screening, baseline, and safety follow-up visit.

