- ^{oo} For MRD analysis a tumor lymph node biopsy and plasma samples will be collected if optional consent is signed. A tumor lymph node biopsy (optional) will be collected at screening, or (when available) archival tissue collected up to 3 months prior to first day of study treatment is acceptable. Plasma samples will be collected on days 1, 19, and 40 pre-dose, and at week 10 (ie, D64), that corresponds to when a subject comes in for disease response assessment, or time of first disease response assessment if done prior to week 10 for cycles 1-2 only. Note: If no lymph node biopsy tissue is collected, then no plasma samples should be collected.
- ^{pp} If blinatumomab is interrupted per Table 6-1, the schedule of assessments will need to be repeated to align with blinatumomab dose. If re-starting at 9 µg/d repeat schedule of assessment procedures starting at D1. If re-starting at 28 µg/d repeat schedule of assessment procedures starting at D8.
- ^{qq} **Serious DREs will be reported through 90 days following cessation of treatment, or 30 days following cessation of treatment if the subject initiates new anticancer therapy (whichever is earlier). Additionally, the investigator must report all fatal DREs.**

**Table 7-4. Schedule of Pembrolizumab Dosing and Related Assessments For Cohorts IIa and IIIa
 (And For Part 2 if MTD is Reached in Either of These Cohorts)**

Pembro- lizumab Cycle	Week	Study Day ^a	Pembrolizumab Dosing ^a	Anti-Pembrolizumab- Antibodies ^b	Pembrolizumab- PK Predose ^c	Pembrolizumab PK Postdose ^d	Thyroid function tests ^e	Chemistry ^e	Hematology/CBC ^e	Urinalysis ^e
Screening	-3 to- 1	-20 to 0					x	x	x	x
Cycle 1	3	19	x	x	x	x	x	x	x	x
Cycle 2	6	40	x	x	x			x	x	
Cycle 3	9	61	x				x	x	x	x
Cycle 4	12	82	x	x	x			x	x	
Cycle 5	15	103	x				x	x	x	x
Cycle 6	18	124	x	x	x			x	x	
Cycle 7	21	145	x				x	x	x	x
Cycle 8	24	166	x	x	x	x		x	x	
Cycle 9	27	187	x				x	x	x	x
Cycle 10	30	208	x					x	x	
Cycle 11	33	229	x				x	x	x	x
Cycle 12	36	250	x	x	x			x	x	
Cycle 13	39	271	x				x	x	x	x
Cycle 14	42	292	x					x	x	
Cycle 15	45	313	x				x	x	x	x
Cycle 16	48	334	x	x	x			x	x	
Cycle 17	51	355	x				x	x	x	x
Cycle 18	54	376	x					x	x	
Cycle 19	57	397	x				x	x	x	x
Cycle 20	60	418	x	x	x			x	x	
Cycle 21	63	439	x				x	x	x	x
Cycle 22	66	460	x					x	x	
Cycle 23	69	481	x				x	x	x	x
Cycle 24	72	502	x	x	x			x	x	
Cycle 25	75	523	x				x	x	x	x
Cycle 26	78	544	x					x	x	
Cycle 27	81	565	x				x	x	x	x

Footnotes defined on the next page of the table

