7.3.10 Bone Marrow Biopsy

A bone marrow biopsy will be performed at screening. Bone marrow biopsy is only required to be repeated with response assessments in case of infiltration or unclear results at screening and in order to confirm a CR. Available results of routine samples will be taken up to 49 days prior to enrollment. Bone marrow biopsy is not required if positron emission tomography (PET) scan is negative in marrow and if not otherwise clinically necessary by investigator discretion.

7.3.11 Core or Incisional/Excisional Biopsy for Biomarker Analysis, MRD by NGS, Cell of Origin, and FISH Analysis (optional)

If as part of the standard institutional procedure, and subject signs the optional consent, a tumor affected lymph node or tissue sample for the diagnosis of relapsed/refractory DLBCL will be collected for subjects enrolled into the study. In addition, a second biopsy is to be collected only in subjects who consent to additional biopsies. Samples should be collected 10 weeks after starting blinatumomab. Sites will process all tissue samples as outlined in the laboratory manual. Submission of formalin-fixed paraffin embedded tumor tissue sample blocks are preferred; slides or fresh frozen tissue are acceptable. All tissue sample preparation guidelines and requirements will be outlined in the laboratory manual.

Tissue will be used for exploratory analyses which may include and not be limited to MRD and immunohistochemistry (IHC). In addition, cell of origin analysis may be performed to determine DLBCL subtypes, and FISH analysis may be performed to determine gene rearrangements associated with double/triple hit DLBCL, if this information is not reported in the CRF under Medical History (see Section 7.3.3).

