7.5.3 MRD by NGS (Next Generation Sequencing)

The presence or absence of MRD is becoming an increasingly important factor in hematologic malignancies and has been a key measure of the depth and quality of the treatment response in other blinatumomab studies. While using circulating tumor DNA (ctDNA) from plasma to measure MRD in DLBCL is a relatively nascent field, studies have suggested inferior outcomes in subjects who have detectable MRD compared to those without detectable disease following treatment (Roschewski et al, 2015). Plasma ctDNA will be used to measure MRD using NGS to analyze gene rearrangements of the B-Cell receptor repertoire. Multiple time points will be analyzed to determine if MRD can be used to monitor early response or progression before disease assessments are obtained. If optional consent is signed, tumor tissue at screening and plasma samples on days 1, 19, 40, and week 10 (ie, day 64), or time of first disease response assessment (if done prior to week 10), will be collected for MRD assessment for cycle 1.

If no lymph node biopsy tissue is collected at screening, then no plasma samples should be collected.

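### MRD plasma is barred without lymph node tissue, although Section 7.3.11 accepts other tumor tissue, so extranodal-only biopsies in cohorts IIa and IIIa would yield no MRD data

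*Protocol*

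**What the plan says.** The rule stands in two places in the protocol. Footnote oo to Table 7-3, the schedule for cohorts IIa and IIIa, closes with "Note: If no lymph node biopsy tissue is collected, then no plasma samples should be collected." Section 7.5.3 closes with "If no lymph node biopsy tissue is collected at screening, then no plasma samples should be collected."

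Other text on the same specimens is wider:

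- Section 7.3.11, whose title names MRD by NGS, says that with optional consent "a tumor affected lymph node or tissue sample for the diagnosis of relapsed/refractory DLBCL will be collected." It lists MRD among the possible uses of that tissue.
- Section 7.5.3, shortly before its closing rule, asks for "tumor tissue at screening and plasma samples on days 1, 19, 40, and week 10," with no nodal limit on the tissue.
- Footnote oo itself says that "archival tissue collected up to 3 months prior to first day of study treatment is acceptable," without naming a site.
- The biopsy row of Table 7-1 (cohort Ia) has no nodal limit. The matching row of Table 7-3 specifies a lymph node biopsy.

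MRD by NGS after cycle 1 is an exploratory endpoint (protocol Section 10.1.1.4, SAP Section 4.1.4). SAP Section 10.5 summarizes it descriptively by cohort on the full analysis set, and SAP Section 9.3 analyzes only non-missing data.

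**The concern.** Two sections describe the tissue that supports MRD as nodal or other tumor tissue, but the rule that releases the plasma draws recognizes only nodal tissue. A site that follows the rule to the letter would take no MRD plasma from a subject who consented and supplied an extranodal biopsy. Pretreatment and early on-treatment plasma cannot be drawn later, so the loss is permanent.

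Whether a subject has MRD data would then depend on where the biopsy was taken. The summary is planned on the full analysis set, and nothing in the SAP tells a reader that it would describe a node-biopsied subset. The protocol also hopes to use MRD to follow early response or progression, and that use would rest on the same subset. No reason is given for the nodal limit.

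**Working it through.** The plan states no sample size or expected count for MRD, so there is no figure to reproduce. The check is a comparison of the text, followed by a count for scale.

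**1. Is lymph node just a loose term for tumor tissue?** Not safely. Section 7.3.11 separates the two with *or*, and Appendix H lists leftover tissue samples and leftover lymph node biopsies as separate items. The unqualified archival tissue in footnote oo points the other way, but the closing sentences of footnote oo and Section 7.5.3 both say lymph node.

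**2. Can a subject with only extranodal tissue enroll?** Inclusion criterion 104 asks for one measurable lesion and does not require it to be nodal. No criterion in Sections 4.1 or 4.2 demands nodal disease or excludes extranodal-only disease. Eligibility is therefore inferred from the absence of a restriction; it is not stated.

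**3. Which subjects and which samples?**

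| | Cohorts IIa, IIIa | Cohort Ia |
|---|---|---|
| Schedule | Table 7-3 | Table 7-1 |
| Lymph node footnote | yes (oo) | none |
| MRD marks in the table | days 1, 19, 40, 64 | screening and day 64 |
| Section 7.5.3 | applies | not excluded, but days 19 and 40 are not Table 7-1 visits |

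The loss of all four plasma time points is clear only for cohorts IIa and IIIa.

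**4. Scale.**

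- Each Part 1 cohort can hold at most 10 subjects, so the two cohorts hold at most 2 × 10 = 20. SAP Section 11 says that Part 2 will not proceed, so no later enrollment is counted.
- The share *s* of subjects with only extranodal tissue is not in the documents. Assume 10% to 40%.
- Expected subjects without MRD plasma = 20 × *s* × (fraction consenting).
- Full consent: 20 × 0.10 = 2 to 20 × 0.40 = 8.
- Half consenting (assumed): 20 × 0.5 = 10 subjects, giving 10 × 0.10 = 1 to 10 × 0.40 = 4.

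The chance that a cohort loses at least one subject is 1 − (1 − *s*)^n. At full consent, *s* from 10% to 40% gives 47% to 95% for a cohort of 6 and 65% to 99% for a cohort of 10. If extranodal-only biopsies are as common as assumed, the rule would probably be met in practice.

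**The case against.** The best defense is that the narrower rule is deliberate. Section 7.3.11 gathers tissue for several purposes and says only that they may include MRD; an assay-specific rule can be stricter than a general collection section. Tissue requirements are deferred to a laboratory manual that is not part of these documents. Requiring some tumor tissue before plasma is also not contradictory in itself. This stands as a caution on the fix: any wider wording must agree with the manual. It does not explain why Section 7.5.3 asks for tumor tissue and then makes plasma conditional on lymph node tissue.

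Selection would also remain after the fix, because tissue is taken only where it is institutional routine and optional consent is signed. That is true, but it is no reason to add selection by biopsy site.

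Some stronger readings are tempting and are not supported:

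- *The loss reaches all of Part 1.* Applying 10% to 40% to the maximum of 30 gives 3 to 12, but this puts cohort Ia on the Table 7-3 schedule and assumes that everyone consents.
- *Subjects with archival tissue lose their plasma too.* This follows only if the at-screening wording of Section 7.5.3 is read apart from footnote oo, which expressly allows archival tissue. The two should be aligned, but together they do not bar these subjects.
- *The SAP baseline row for extranodal disease shows that extranodal-only subjects are expected.* A subject can have both nodal and extranodal disease, and the row says nothing about biopsy site.

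**Conclusion.** The inconsistency is real. For cohorts IIa and IIIa the stated rule, followed literally, removes a consenting subject with only an extranodal biopsy from a named exploratory endpoint, and the plasma cannot be recovered. An illustrative size is 2 to 8 of at most 20 subjects. It rests on an assumed 10% to 40% share, full consent, both cohorts expanded to 10, and eligibility of extranodal-only disease, which is inferred. Partial consent or smaller cohorts lower it. For cohort Ia the documents do not settle the effect.

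A reader might infer that the trial's efficacy or safety conclusions are at risk. They are not: no DLT, response rate or stopping decision uses MRD, and the analysis is descriptive. This is a minor point that is easily corrected.

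**What to change.** In footnote oo and in the last sentence of Section 7.5.3, make plasma collection conditional on *tumor tissue (nodal or extranodal, including archival tissue within the stated 3 months)*, subject to the tissue requirements in the laboratory manual. Align the at-screening wording of Section 7.5.3 with the archival allowance in footnote oo. If the nodal limit is intended, say so and give the reason.

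If collection is already complete, report MRD with a denominator of subjects who have evaluable tissue and plasma, by cohort, and tabulate why plasma was not collected in the others.

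The cost is a wording change in two places and a few more plasma assays. The draws are already scheduled for consenting subjects in cohorts IIa and IIIa.

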7.2 General Study Procedures

7.2.1 Screening and Enrollment

Screening procedures are to be completed during the screening time period at the times designated in the Schedule of Assessments ([Table 7-1](#), [Table 7-2](#), [Table 7-3](#), and [Table 7-4](#)).

All subjects or their legally acceptable representative (ie, legal guardian) must sign and date the most current IRB/IEC approved ICF. Confirmation that the ICF has been signed should occur before any study specific procedures are performed.

All subjects who are enrolled and receive protocol-specified therapy should be re-consented with any updated versions of IRB/IEC approved informed consents during study participation applicable and per institutional guidelines.

7.2.2 Treatment

The following procedures will be completed during the treatment period at the times designated in the Schedule of Assessments ([Table 7-1](#), [Table 7-2](#), [Table 7-3](#), and [Table 7-4](#)). Administration of protocol-required therapies is to be administered last during each visit that it is required.

- Physical Examination
- PK (including intensive PK assessments)
- Vital signs (eg, blood pressure, heart rate, respiration rate, temperature)
- Laboratory Assessments including local and central laboratories, as applicable
- Imaging Assessments
- Serious Adverse Event reporting
- Adverse Event reporting
- Disease Related Event Reporting
- Documentation of concomitant medications
- Receipt of protocol-required therapies

If a subject stops treatment (eg, due to an adverse event), the investigator must ensure there is a plan for continued follow-up until the subject completes all protocol-required visits or withdraws from the study.

7.2.3 Safety Follow-up Visit

All subjects will complete a safety follow-up visit approximately 30 (+ 7) days after the last dose of each study treatment. Serious adverse events (and any concomitant medications associated with serious adverse events) observed by the investigators or reported by the subjects that occur within 90 (+7) days after the cessation of all study treatment or 30 (+7) days following cessation of treatment if the subject initiates new anticancer therapy (whichever is earlier) will be reported, followed, and recorded.

For all subjects, 2 safety follow-up visits should be performed: 30 days (+ 7 days) after the last dose of blinatumomab and 30 days (+ 7 days) after the last dose of pembrolizumab.

If a subject starts a new anti-lymphoma treatment within 30 days of their last dose of protocol-assigned therapy, a safety follow-up visit should be conducted immediately prior to starting any new treatment, including HSCT conditioning regimens.

7.2.4 Long-term Follow-up

After the safety follow-up visit, all subjects will enter long-term follow-up. Subjects who end blinatumomab treatment but continue pembrolizumab monotherapy will be considered to be in long-term follow-up. Subjects will be followed for survival and subsequent anticancer therapies every 12 weeks (\pm 28 days) following blinatumomab safety follow-up visit until approximately 24 months from the last dose of pembrolizumab. In case that a subject continues pembrolizumab monotherapy (and until monotherapy ends), this long-term follow-up schedule will occur in parallel with the schedule of assessments of pembrolizumab dosing and related assessments. **Serious adverse events that occur through 90 days following cessation of treatment, or 30 days following cessation of treatment if the subject initiates new anticancer therapy, whichever is earlier, will be collected and reported. After this period, SAEs suspected to be related to IP, and fatal SAEs (regardless of causality) will be collected and reported.**

7.2.5 End of Study

The end of study for each subject is defined as the date the subject withdraws full consent from the study, completes the final safety follow-up visit or final long-term follow-up visit (whichever is later) or death.

7.3 Description of Study Procedures

An overview of study assessments/procedures is provided below. Refer to the eCRF completion guidelines for data collection requirements and documentation of study assessments/procedures.

7.3.1 Informed Consent

All subjects or their legally acceptable representative (ie, legal guardian) must sign and date the most current IRB/IEC approved ICF. Confirmation that the ICF has been signed should occur before any study specific procedures are performed.

All subjects who are enrolled and/or receive protocol-specified therapy should be re-consented with any updated versions of IRB/EC approved informed consents during study participation as applicable and per institutional guidelines.

In countries where foreign subjects can be enrolled according to local regulations (agreement by responsible IRB/IEC required), specific requirements for the process of consenting subjects as well as for the conduct of the study visits will apply. It is the investigator's responsibility to ensure that the subject will understand the ICF and that the subject will be able to communicate appropriately with the investigator, study team, and ambulant care service provider, if applicable (eg, by translation of the ICF into the subject's native language and providing an interpreter, as applicable). The investigator should also highlight the importance of attending applicable follow-up visits and collection of Long-Term Follow-up data (eg, overall survival (OS), additional anticancer therapy) to all subjects during the informed consent process.

7.3.2 Demographics

Demographic data that will be collected include sex, date of birth, and ethnicity to study their possible association with subject safety and treatment effectiveness.

7.3.3 Medical History

The investigator or designee will collect a complete medical and surgical history that started 5 years prior to screening through the time of enrollment. Medical history will include information on the subject's concurrent medical conditions. Diffuse large B-cell lymphoma history must date back to the initial diagnosis.

In addition to the medical history noted above, all history related to the subject's diagnosis of DLBCL (eg, date of initial diagnosis, additional risk factors at diagnosis, cell-of-origin [COO] at any timepoint if available [immunohistochemistry pattern, GEP/other], BCL-2 fluorescence in situ hybridization (FISH): translocation,

immunohistochemistry expression levels], c-myc [FISH: translocation, immunohistochemistry expression levels]) will be recorded.

7.3.4 ECOG Performance Status

Assessment of the subject's performance status will be performed at screening and 30 days after each treatment end using the ECOG score (see [Appendix D](#)).

7.3.5 Physical Examination

Physical examinations will be completed as per standard of care. All clinically relevant findings will be documented. Physical examination will also include a neurological exam. Body height (only at screening) and weight will also be documented. Body temperature (eg, oral or tympanic), supine heart rate, and blood pressure (systolic/diastolic) will be measured at regular intervals during the study. The investigator should monitor the subject's vital signs continuously every 4 hours during the first 12 hours after the start of each new blinatumomab treatment/dose step. Vital sign measurements will be repeated daily during the subject's hospitalization.

7.3.6 Neurological Examinations

Any neurological abnormalities observed in neurological examinations or reported by the subject after enrollment are to be recorded as each individual event in the event log such as: level of consciousness, orientation, vision, cranial nerves and brain stem functions, pyramidal and extra pyramidal motor system, reflexes, muscle tone and trophic findings, coordination, sensory system, and neuropsychological findings, (eg speech, cognition, and emotion). A neurological exam should also be performed in the case of grade 3 or higher neurologic events (**Appendix F**).

7.3.7 Hepatitis B Antigen, Anti-Hepatitis B core Antigen, and Anti-Hepatitis B Surface Antigen

Hepatitis b surface (HBs) antigen, HBs antibody, and hepatitis b core (HBc) antibody will be tested at screening for all subjects. For subjects with history of seronegative HBV exposure or indeterminate HBV status (anti-Hbc antibody positive, anti-HBs antibody negative, and anti-HBs antigen negative), HBV DNA viral load should be performed at screening and at regular intervals during blinatumomab treatment to monitor for HBV re-activation.

